4.2.2 Secondary endpoints

- **Progression-free survival (PFS)** will be measured from the date of treatment initiation to the date of event defined as the first documented disease progression or death from any cause. Patients with no event at the time of analysis will be censored at the date of last adequate tumor assessment. The date of first progression will be determined using data from the tumor evaluation form.
- **Overall survival (OS)** will be measured from the date of treatment initiation to the date of death from any cause. Patients who are alive at the time of analysis will be censored at the date of last contact. Number of patients deceased and cause of death will be reported.

PFS and OS will be estimated using the Kaplan-Meier method. Survival curves will be plotting according to p4EBP1 (high vs low) and compared using a logrank test.

A Cox proportional hazards model will be performed to explain the progression-free survival time. Variables sufficiently informed (less than 10% missing values) and significant at a 15% level in a univariate approach will be included in a backward selection procedure to keep factors significant at a 5% level in the final multivariate model. Hazard ratios (HRs) will be presented with their 95% confidence intervals (CI).

- The clinical benefit rate at 6 months will be described with its 95% confidence interval according to:
 - the presence/absence of each studied genomic event
 - the expression levels of each studied proteomic biomarker (cutoff will be defined in the same way as mentioned for the primary endpoint)
- Descriptive statistics will be used to **characterize the molecular landscape** of endocrine-resistant disease in terms of genomic events observed. Correlations between the different types of genomic events will be studied.

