2.2.2 Secondary endpoints

- Predictive value of genomic events in determining mTOR inhibitor efficacy where genomic events are defined as mutations, amplifications, gains, and losses.
- Predictive value of protein biomarkers (pTEN, AKT, pSRB, LKB1) in determining mTOR inhibitor efficacy.
- Molecular landscape of endocrine-resistant disease, in particular correlations between genomic events observed

3 General statistical methods and analysis population definition

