4.2 Efficacy endpoint

4.2.1 Primary endpoint

For the primary endpoint, the analysis will be performed on the efficacy population and will include all treated and evaluable patients. A patient will be considered as evaluable if 1) no major violation of eligibility criteria, 2) the patient has received at least one dose of everolimus, 3) the patient has at least one tumor evaluation performed before and another 6 months after treatment initiation and 4) an expression levels of p4EBP1 is available for the patient. The clinical benefit rate at 6 months (CBR-6m) will be defined as the proportion of patients with a complete response, a partial response, or a stable disease 6 months after initiation of treatment. The CBR-6m and its associated 95% confidence interval (CI) will be described globally and according to high vs low p4EBP1 expression, and will be compared between the 2 subgroups using a chi-square test. In the absence of assumptions, the choice of cut-off for dichotomized the population depending on p4EBP1 values will be done using the median value of the biomarker distribution, the aim being to consolidate data into subgroups of comparable strengths to maximize the power. A second cut-off will be determined using the X-tile software, proposing a division of the population for an optimal separation of data seeing the responses. This second analysis will be considered as a sensitivity analysis.

Logistic regression analyses will be performed to assess the predictive potential effect of biomarker level on clinical benefit rate at 6 months (Yes/No). Clinical factors known to be predictive of clinical benefit will be added to the model to verify the independence of the marker. A step-by-step descending selection of variables will be used to retain factors that were independently linked to clinical benefit. All variables sufficiently informed (with <10% missing value) and significant (at 15% level) in the univariate approach will be introduced in the initial multivariate model. The final multivariate model will be include only variables which will be statistically significant at a 5% threshold. Odd ratio (OR) will be presented with 95% confidence interval (CI). A p-value <0.05 will be considered statistically significant.

For each patient, the variable "clinical benefit rate at 6 months Yes/No" will be determined as follows:

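### Section 4.2.2 gives each secondary marker a separate CBR-6m with CI per subgroup, but plans no between-group effect with an interval, which the marker endpoints in section 2.2.2 call for

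*SAP*

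**What the plan says.** Section 2.2.2 names two marker endpoints besides the molecular landscape: "Predictive value of genomic events in determining mTOR inhibitor efficacy where genomic events are defined as mutations, amplifications, gains, and losses" and "Predictive value of protein biomarkers (pTEN, AKT, pSRB, LKB1) in determining mTOR inhibitor efficacy".

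The matching analysis in section 4.2.2 reads "The clinical benefit rate at 6 months will be described with its 95% confidence interval according to", followed by two groupings. One is "the presence/absence of each studied genomic event"; the other is the expression level of each protein marker. For the proteins, one element is carried over from the primary analysis: "cutoff will be defined in the same way as mentioned for the primary endpoint".

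For p4EBP1, section 4.2.1 goes further. After the rates and intervals by subgroup, CBR-6m "will be compared between the 2 subgroups using a chi-square test". A logistic model then gives an odds ratio with a 95% CI. On the covariates of that model the SAP says: "Clinical factors known to be predictive of clinical benefit will be added to the model to verify the independence of the marker".

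**The concern.** Whether a marker bears on benefit is a question about the difference between marker groups. The plan estimates the two rates separately and stops there. No effect measure is chosen for the contrast, and no interval for it is planned.

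At stake are two of the three endpoints in section 2.2.2. If the plan is followed to the letter, the report will show pairs of rates with intervals. Readers of such tables tend to check whether the intervals overlap, and that is a poor guide to whether the groups differ. If someone computes a contrast later, the choice of measure and of markers will be made after the data are known, across an unstated number of genomic events.

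**Working it through.** **1. Is a contrast on CBR-6m planned anywhere for these markers?** Going through the SAP:

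| Analysis | Place | Covers genomic events or the other proteins on CBR-6m? |
|---|---|---|
| Chi-square test | 4.2.1 | No, p4EBP1 subgroups only |
| Logistic regression, OR with CI | 4.2.1 | No, p4EBP1 plus clinical factors |
| Logrank test | 4.2.2 | No, by p4EBP1; PFS and OS |
| Cox model | 4.2.2 | Candidates not named; outcome is PFS |
| Correlations | 4.2.2 | No, among genomic events |
| CBR-6m with 95% CI | 4.2.2 | Yes, but within each subgroup only |

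No contrast is planned.

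**2. The plan's own figure.** Section 3.1 gives 80% power with 60 per group, two-sided 0.05, for an odds ratio of 2.8 (30-40% against 55-65%). With pooled variance and no continuity correction,

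power = Φ{ [ |p2 − p1|·√n − 1.96·√(2·p̄·(1 − p̄)) ] / √( p1(1 − p1) + p2(1 − p2) ) }.

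For 35% against 60%: (0.25 × 7.746 − 1.96 × 0.706) / 0.684 = 0.808, so power is 79.0%. For 30% against 55% it is 79.9%, and for 40% against 65% it is 79.0%. The stated 80% is sound, and the point does not depend on it.

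**3. Overlapping intervals with a contrast that excludes no effect.** The counts are illustrations. N = 120 comes from section 3.1; the 20% marker frequency is an assumption, since the SAP gives none. The SAP names no interval method for the rates, so exact (Clopper-Pearson) limits are used. For the odds ratio, SE(ln OR) = √(1/a + 1/b + 1/c + 1/d).

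*20% frequency, 15/24 against 36/96.*
- Rates: 62.5% (40.6 to 81.2) and 37.5% (27.8 to 48.0). The intervals overlap.
- OR = (15 × 60)/(9 × 36) = 2.78.
- SE = √(1/15 + 1/9 + 1/36 + 1/60) = 0.471.
- 95% CI = exp(1.022 ± 1.96 × 0.471) = 1.10 to 7.00.
- Chi-square p = 0.027; Fisher exact p = 0.037.

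*Equal split, 33/60 against 21/60.*
- Rates: 55.0% (41.6 to 67.9) and 35.0% (23.1 to 48.4). The intervals overlap.
- OR = (33 × 39)/(27 × 21) = 2.27.
- SE = √(1/33 + 1/27 + 1/21 + 1/39) = 0.375.
- 95% CI = exp(0.820 ± 1.96 × 0.375) = 1.09 to 4.73.
- Difference 20 points (Newcombe 95% CI 2.2 to 36.1); chi-square p = 0.028.

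**4. How often does this happen?** Take true rates of 60% and 35%, within the ranges in section 3.1. Sum the binomial probabilities over all outcomes in which the two exact intervals do not overlap, and separately over those in which the chi-square test gives p < 0.05.

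| Split | Intervals do not overlap | Chi-square p < 0.05 |
|---|---|---|
| 60/60 | 41% | 80% |
| 24/96 | 26% | 61% |

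A reader who went by overlap would miss about half or more of the differences that a direct comparison finds.

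**The case against.** The strongest reply is that description is deliberate. Section 4.2.1 both describes and compares, while section 4.2.2 only describes. That looks like inference kept for the one powered hypothesis. The restraint has a reason: unadjusted 0.05 tests on 4 independent markers carry a family-wise error of 1 − 0.95⁴ = 18.5%, and on 20 markers 64%. This stands as an argument against formal tests. It is no argument against an effect estimate with an interval, which is itself descriptive.

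Several stronger readings are tempting, and the document does not support them:

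- *That the plan judges markers by overlap of intervals.* It states no such rule, and no decision rule at all for these markers. The overlap figures show only what an informal reading would cost.
- *That no effect estimate or ranking can be had.* The reported rates give a point difference or odds ratio directly, and with the counts an interval can be computed as well. What is missing is the commitment to do so and the choice of measure.
- *That a marker with the design effect would always look inconclusive.* At 36/60 against 21/60 the exact intervals (46.5 to 72.4 and 23.1 to 48.4) overlap by only about two points. A reader could well see a difference there.
- *That adjusted p-values or a minimum event frequency are needed.* Those are preferences, and they bring in testing that the SAP seems to avoid.

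The unnamed Cox candidates might include these markers. The SAP does not say so, and the outcome would be PFS rather than CBR-6m. A protocol that is not at hand does not settle the matter either, because the SAP itself states the analysis for these endpoints.

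**Conclusion.** The point holds as a mismatch within the SAP. Two secondary endpoints ask about a relation between marker and benefit, and the stated analysis gives separate subgroup rates without an interval for the contrast. The primary analysis is unaffected, and the gap can be closed from data already planned.

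The textual finding needs no assumption. Its size does: the illustrative counts, the 20% frequency, rates of 60% and 35% for the overlap probabilities, and exact intervals for the rates. The 20% example also carries only modest evidence, with an interval that starts at 1.1.

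A reader might infer that adding a contrast would establish predictive value. It would not. The SAP describes patients treated with everolimus plus exemestane and no comparator, so a contrast shows association with benefit on treatment and cannot separate predictive from prognostic value.

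**What to change.** In section 4.2.2, keep the planned subgroup rates and add one sentence along these lines: for each genomic event (present vs absent) and each protein marker (high vs low), the odds ratio or the rate difference for clinical benefit at 6 months will be given with its 95% CI, by an exact method where data are sparse, and labelled exploratory. Choose one of the two measures before the data are analysed. Formal tests are not required; if p-values are reported, state how multiplicity is handled.

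The cost is a few lines of SAP text and a little more programming, with no new data. The downside is a larger set of exploratory estimates to interpret, many of them imprecise for rare events. At an assumed 10% frequency, for example, 7/12 against 38/108 gives an odds ratio of 2.58 with a 95% CI of 0.77 to 8.68. Reporting that width is better than leaving it to be guessed from two intervals.

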4.3 Description of safety data

All patients who have received the study treatment (exemestane or everolimus) will be included in the safety analysis.

Number of patients (count, %) with:

- At least one grade >= 3 AE
- At least one related grade >= 3 AE
- At least one SAE
- At least one SAE related to study treatment
